## **2.0 INTRODUCTION**

This Statistical Analysis Plan (SAP) describes the methodology that will be used to summarize the statistical analyses of the efficacy and safety data for the final protocol Amendment 2 of Study RAP-MD-04 (version dated 13 Nov 2018).

Study RAP-MD-04 is a multicenter, double-blind, randomized, placebo-controlled, parallel-group study to evaluate the efficacy, safety, and tolerability of rapastinel as long-term maintenance treatment for patients with major depressive disorder (MDD) who completed 1 of the rapastinel lead-in studies (RAP-MD-01, RAP-MD-02, or RAP-MD-03). While the protocol was written to accommodate the potential recruitment of *de novo* patients, there were no *de novo* patients enrolled. Consequently, all analysis in this document pertains specifically to roll-over patients only.

The study will be conducted for the roll-over patients in the following periods:

- An 8- to 16-week, open-label treatment period (OLTP) where patients receive rapastinel 450 mg IV weekly
- A randomized, double-blind treatment period (DBTP) of at least 26 weeks (and up to 104 weeks) where patients are randomized 1:1:1 to either rapastinel 450 mg weekly, rapastinel 450 mg biweekly or placebo
- A 2-week safety follow-up period (for patients who do not enter the RAP-MD-06 extension study only)

In order for patients to transition from the OLTP and be randomized into the DBTP, the patient must meet the stable responder criterion sometime after 8 weeks (and up to 16 weeks) during the OLTP. A patient will be considered a stable responder upon achieving both criteria (1) and (2) below:

- 1) An observed Montgomery-Asberg Depression Rating Scale (MADRS) total score  $\leq 12$  with no more than one modest MADRS excursion (MADRS total score  $> 12$  but  $\leq 16$ ) for at least 6 consecutive weeks.
- 2) An observed MADRS total score  $\leq 12$  for at least 2 consecutive visits prior to randomization.

To meet these criteria a patient must have no missing MADRS assessments within the last 6 consecutive weeks prior to randomization.

The OLTP starts with the first dose of open-label treatment and ends with 1 of the following: the last scheduled assessment at the Visit 122/Early Termination for patients who do not enter the DBTP; the first dose of double-blind treatment for patients who enter the DBTP.

[figure not shown]

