The double-blind treatment period starts when the first dose of double-blind treatment is administered and ends with the last scheduled assessment at Visit 122 (or ET).

[figure not shown]
For patients not entering RAP-MD-06, the safety follow-up (SFU) period starts after completion of the last scheduled assessment at Visit 122 (or ET) and ends with the last available assessment.

[figure not shown]
Individual treatment durations will vary, as patients enrolled early in the study will be allowed to continue treatment in the DBTP until a relapse occurs or the study is terminated. The maximum duration of the study will be 104 weeks (the study ends when all randomized patients have either met relapse criteria, early terminated for other reasons, or completed 26 weeks of the DBTP).

[figure not shown]

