## 9.1 ADVERSE EVENTS

AEs will be coded using the *Medical Dictionary for Regulatory Activities*.

An AE (classified by preferred term) that occurs during the OLTP or thereafter will be considered a treatment-emergent adverse event (TEAE) if it was not present before the date of the first dose of IP in the lead-in study or was present before the first dose of IP in the lead-in study and increased in severity during the OLTP or thereafter. An AE that becomes serious during the OLTP or thereafter will also be considered as a TEAE. If more than 1 AE is reported before the date of the first dose of IP in the lead-in study and coded to the same preferred term, the AE with the greatest severity will be used as the benchmark for comparison with the AEs occurring during the OLTP or thereafter that were also coded to that preferred term. An AE that occurs more than 30 days after the date of the last dose of IP will not be counted as a TEAE.

An AE (classified by preferred term) that occurs during the OLTP of the study will be considered a newly emergent adverse event (NEAE) if the AE was not present before the first dose of IP in the OLTP or it was present before the first dose of IP in the OLTP and increased in severity during the OLTP. An AE that becomes serious during the OLTP will also be considered as an NEAE. If more than 1 AE is reported before the first dose of IP in the OLTP and coded to the same preferred term, the AE with the greatest severity will be used as the benchmark for comparison with the AEs occurring during the OLTP that were also coded to that preferred term.

An AE (classified by preferred term) that occurs during the DBTP of the study will be considered an NEAE if the AE was not present before the first dose of IP in the DBTP or it was present before the first dose of IP in the DBTP and increased in severity during the DBTP. An AE that becomes serious during the DBTP will also be considered as an NEAE. If more than 1 AE is reported before the first dose of IP in the DBTP and coded to the same preferred term, the AE with the greatest severity will be used as the benchmark for comparison with the AEs occurring during the DBTP that were also coded to that preferred term.

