An AE (classified by preferred term) that occurs during the SFU of the study will be considered an NEAE if the AE was not present before or at Visit 122 or it was present before or at Visit 122 and increased in severity during the SFU. An AE that becomes serious during the SFU will also be considered as an NEAE. If more than 1 AE is reported before or at Visit 122 and coded to the same preferred term, the AE with the greatest severity will be used as the benchmark for comparison with the AEs occurring during the SFU that were also coded to that preferred term.

An AE that occurs more than 30 days after the date of the last dose of IP will not be counted as an NEAE.

The number and percentage of patients reporting TEAEs and NEAEs during the OLTP will be tabulated overall by SOC and preferred term. The number and percentage of patients in each treatment group reporting TEAEs and NEAEs during the DBTP and during the SFU will be tabulated by SOC and preferred term; by SOC, preferred term, and severity; and by SOC, preferred term, and causal relationship to the IP. If more than 1 AE is coded to the same preferred term for the same patient during the same treatment period, the patient will be counted only once for that preferred term using the most severe and most related occurrence for the summarization by severity and by causal relationship to the IP.

[figure not shown]
The incidence of common ( $\geq 2\%$  of patients in any treatment group) TEAEs and NEAEs during the OLTP will be summarized overall by preferred term. Similarly, the incidence of common TEAEs and NEAEs during the DBTP and during the SFU will be summarized by preferred term and treatment group and will be sorted by decreasing frequency starting with the weekly rapastinel group followed by the biweekly rapastinel group.

[figure not shown]
An SAE that occurred between the date of the first dose of IP in the OLTP and 30 days after the date of the last dose of IP, inclusive, will be considered a treatment-emergent SAE (TESAE). The number and percentage of patients who had TESAEs during the OLTP will be summarized overall by preferred term and sorted by decreasing frequency. The number and percentage of patients who had TESAEs during the DBTP and during the SFU will be summarized by treatment group and preferred term and will be sorted by decreasing frequency starting with the weekly rapastinel group followed by the biweekly rapastinel group.

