### **Missing month and day**

- If the year of the incomplete start date is the same as the year of the first dose of open-label IP, the month and day of the first dose of open-label IP will be assigned to the missing fields.
- If the year of the incomplete start date is before the year of the first dose of open-label IP, *31 Dec* will be assigned to the missing fields.
- If the year of the incomplete start date is after the year of the first dose of open-label IP, *01 Jan* will be assigned to the missing fields.

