### **Missing day only**

- If the month and year of the incomplete start date are the same as the month and year of the first dose of open-label IP, the day of the first dose of open-label IP will be assigned to the missing day.
- If either the year of the incomplete start date is before the year of the date of the first dose of open-label IP or if both years are the same, but the month of the incomplete start date is before the month of the date of the first dose of open-label IP, the last day of the month will be assigned to the missing day.
- If either the year of the incomplete start date is after the year of the date of the first dose of open-label IP or if both years are the same, but the month of the incomplete start date is after the month of the date of the first dose of open-label IP, the first day of the month will be assigned to the missing day.

If the stop date is complete and the imputed start date as above is after the stop date, the start date will be imputed by the stop date.

If the start date is completely missing and the stop date is complete, the following algorithm will be used to impute the start date:

- If the stop date is after the date of the first dose of open-label IP, the date of the first dose of open-label IP will be assigned to the missing start date.
- If the stop date is before the date of the first dose of open-label IP, the stop date will be assigned to the missing start date.

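### Section 15.7 dates incomplete AE starts from the first open-label dose only, so in randomized patients a start that fits both periods always falls in the OLTP and leaves the by-arm DBTP NEAE tables unless the AE worsens or becomes serious

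*SAP*

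**What the plan says.** Section 2.0 sets the period boundary. For randomized patients the OLTP ends with "the first dose of double-blind treatment for patients who enter the DBTP", and "The double-blind treatment period starts when the first dose of double-blind treatment is administered".

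Section 9.1 uses the same boundary for newly emergent events: an AE in the DBTP "will be considered an NEAE if the AE was not present before the first dose of IP in the DBTP", or if it was present earlier and then increased in severity or became serious during the DBTP. The tables built on this give the number and percentage of "patients in each treatment group reporting TEAEs and NEAEs during the DBTP".

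Section 15.7 imputes incomplete AE start dates, and each of its rules looks only at the first open-label dose:

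- **Only the year known, same year as that dose:** "the month and day of the first dose of open-label IP will be assigned to the missing fields". A later year becomes 1 January of that year.
- **Day missing, calendar month after that dose:** the rule ends "of the first dose of open-label IP, the first day of the month will be assigned to the missing day".
- **Start wholly missing, complete stop date after that dose:** "the date of the first dose of open-label IP will be assigned to the missing start date".

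The one override in Section 15.7 resets an imputed start to the stop date when the start would fall after it. That moves a start earlier, never forward into the DBTP.

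**The concern.** The event that separates the two periods never enters the imputation. Suppose the surviving date information fits both the OLTP and the DBTP. The rules then choose the OLTP every time. The AE counts as present before the first double-blind dose and moves from the by-arm DBTP NEAE tables to the overall OLTP tables, unless it later increases in severity or becomes serious.

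The by-arm DBTP tables carry the placebo-controlled safety comparison, whereas the OLTP tables have no comparator. The displacement runs one way, as an under-count of DBTP NEAEs. There is also a knock-on effect. Under Section 9.1 the most severe earlier AE of the same preferred term is the benchmark for DBTP events, so a misplaced AE can keep a later DBTP event of equal or lower severity from counting.

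**Working it through.** The plan states no figure on this point, so there is none to reproduce. The check applies Section 15.7 literally.

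**Inputs from the SAP.** OLTP of 8 to 16 weeks and DBTP of 26 to 104 weeks (Section 2.0); the start-date rules (Section 15.7).

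**Assumptions, not in the SAP.** First open-label dose uniform over the calendar year; AE onset uniform over the DBTP.

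**Step 1: illustrative patients.** First open-label dose 10 Mar 2017, first double-blind dose 14 Jun 2017.

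| Recorded start | Imputed start | Period assigned |
|---|---|---|
| Jun 2017 | 1 Jun 2017 | OLTP |
| 2017 | 10 Mar 2017 | OLTP |
| none, stop 1 Sep 2017 | 10 Mar 2017 | OLTP |

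The last AE stopped 79 days (about 11 weeks) into the DBTP. The same happens across a year end: with doses on 10 Nov 2017 and 19 Jan 2018, a start recorded as 2018 or as Jan 2018 becomes 1 Jan 2018, in the OLTP.

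**Step 2: share of true DBTP onsets placed in the OLTP.** Share = onsets imputed before the first double-blind dose ÷ all DBTP onsets. Every one of 365 open-label dose dates was combined with every DBTP day, for OLTP lengths of 8, 12 and 16 weeks. The results were identical for the three lengths.

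| Missing part | 26 weeks (365 × 183 = 66,795 onsets) | 52 weeks (365 × 365 = 133,225 onsets) |
|---|---|---|
| Day | 5,373 / 66,795 = 8.0% | 5,373 / 133,225 = 4.0% |
| Month and day | 49,959 / 66,795 = 74.8% | 66,430 / 133,225 = 49.9% |
| Whole start, stop date complete | 100% (by rule) | 100% (by rule) |

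Every onset whose remaining information fitted both periods went to the OLTP. None that fitted only the DBTP was moved, so day-missing AEs in later months are placed correctly. A simulation of 400,000 patients, with the OLTP running 56 to 112 days (mean 84), gave 8.1/4.0/2.0% for day-missing and 75/50/25% for year-only dates over 26/52/104 weeks.

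**Step 3: absolute size.** Absolute share = rate of incomplete dates × share in Step 2. The SAP gives no such rate. If 1% to 10% of AEs lacked only the day (assumption), the range is 0.01 × 2.0% = 0.02% to 0.10 × 8.1% = 0.8% of DBTP-onset AEs. These are shares of AEs. The tables count a patient once per preferred term, so the shares do not convert directly into table percentages.

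**Step 4: effect of a second anchor.** Take an equal AE rate per day in both periods, 84 OLTP days plus 182 DBTP days = 266 days' worth of onsets, complete stop dates, and exponential AE durations with mean 3 to 28 days (assumption).

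| Missing part | DBTP days recovered | OLTP days moved in | Net gain, days | Wrong period now | Wrong period after |
|---|---|---|---|---|---|
| Day | 14.8 | 2.3 to 10.4 | 12.5 to 4.4 | 14.8 / 266 = 5.6% | 0.8 to 3.9% |
| Month and day | 136.4 | 2.5 to 24.2 | 133.9 to 112.2 | 136.4 / 266 = 51.3% | 1.0 to 9.1% |
| Whole start | 182 | 2.6 to 25.9 | 179.4 to 156.1 | 182 / 266 = 68.4% | 1.0 to 9.7% |

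If nearly all OLTP AEs ran past the first double-blind dose, the day-missing exchange would be 14.7 days moved in against 14.8 recovered, a net gain of about zero. The daily AE rate in the OLTP would have to exceed that in the DBTP by a factor of 5.6 to 54 (year-only) or 7.0 to 71 (no start) before the second anchor did net harm. For day-missing dates the factor is only 1.4 to 6.5.

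**The case against.** Section 15.7 can be executed as written and contradicts nothing. Its anchor matches Sections 15.5, 15.6 and 15.8.1. Section 15.8.2 does use the last double-blind dose, but for medication stop dates, which is a different variable. The large shares belong to patterns that should be uncommon with the weekly visits of Table 15.2–2. Displaced events are not lost, since they stay in the overall OLTP tables. A second anchor has its own error: it would bring AEs that began on open-label rapastinel into the by-arm tables, the placebo column included. For day-missing dates, the month of the first double-blind dose is on average about half OLTP and half DBTP, so the choice of anchor is close to a preference when AEs last long.

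Most of this stands, and it is why the point is minor and why day-missing dates are treated as optional below. It does not rescue the wholly-missing-start rule. Dating an AE that stopped months into the DBTP to the first open-label day is the least plausible reading of the data, and there the second anchor gains far more than it costs.

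A reader might infer more than the document supports:

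- **That the arms are compared unfairly.** The rule is the same in all arms, and nothing in the SAP suggests that incomplete dates differ by arm.
- **That these AEs can never appear in the DBTP tables.** Section 9.1 readmits those that worsen or become serious.
- **That treatment-emergent status changes.** It is judged against the first dose in the lead-in study.
- **That most DBTP AEs disappear.** The 75% and 100% apply only to AEs with those patterns of missing dates.

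**Conclusion.** The point holds and is minor. In randomized patients, Section 15.7 always resolves an ambiguous AE start date to the OLTP, although Sections 2.0 and 9.1 make the first double-blind dose the dividing line. The result is an under-count of DBTP NEAEs in all arms. It is clearest for wholly missing starts (100% by rule, given a complete stop date after the first open-label dose), next for year-only dates (about 75/50/25% of DBTP onsets over 26/52/104 weeks), and least for day-missing dates (about 8/4/2%).

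The year-only and day-missing shares rest on uniform entry and uniform onset. Without a stated rate of incomplete dates the absolute effect is unknown and probably small. The efficacy tests and the listings of SAEs, deaths and AEs leading to discontinuation are not affected.

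**What to change.** Add the first double-blind dose to Section 15.7 as a second anchor for randomized patients:

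- If the known date parts allow onset on or after the first double-blind dose, and the complete stop date is on or after that dose, impute the later of the current rule's date and the first double-blind dose date.
- Otherwise keep the current rule. This includes missing stop dates, ongoing AEs and patients who were not randomized.
- Apply this first to wholly missing and year-only starts. For day-missing dates it is optional, because the gain is small and nears zero when AEs last long.

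The change costs SAP wording and programming only, with two downsides to accept openly:

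- **OLTP onsets moved into the DBTP.** For assumed mean durations of 3 to 28 days, about 3 to 13% of day-missing, 3 to 30% of year-only and 3 to 32% of missing-start OLTP onsets would be counted in the DBTP in every arm. In the placebo arm these are events that began on open-label rapastinel.
- **Safety follow-up onsets.** In that period an AE "will be considered an NEAE if the AE was not present before or at Visit 122"; this boundary is outside the change. Follow-up AEs with no start date but a complete stop date, and about 48% of year-only ones at 26 weeks, now fall in the OLTP and would move to the DBTP, which is also the wrong period. The follow-up lasts only 2 weeks, so few events should be involved.

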## 15.8 MISSING DATE INFORMATION FOR PRIOR OR CONCOMITANT MEDICATIONS

For prior or concomitant medications, including background ADT, incomplete (ie, partially missing) start dates and/or stop dates will be imputed. When the start date and the stop date are both incomplete for a patient, the start date will be imputed first.

### 15.8.1 Incomplete Start Date

The following rules will be applied to impute the missing numeric fields for an incomplete prior or concomitant medication start date. If the stop date is complete (or imputed) and the imputed start date is after the stop date, the start date will be imputed using the stop date.

#### Missing month and day

- If the year of the incomplete start date is the same as the year of the first dose of open-label IP, the month and day of the first dose of open-label IP will be assigned to the missing fields.
- If the year of the incomplete start date is before the year of the first dose of open-label IP, 31 Dec will be assigned to the missing fields.
- If the year of the incomplete start date is after the year of the first dose of open-label IP, 01 Jan will be assigned to the missing fields.

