#### **Efficacy Objectives**

- **Primary efficacy objective:** To evaluate the efficacy of rapastinel (450 mg IV weekly or once every 2 weeks) versus placebo in the maintenance treatment of MDD as an adjunctive treatment to ongoing antidepressant therapy (ADT), as measured by time to relapse during the first 52 weeks of the DBTP
- **Secondary efficacy objective:** To evaluate the efficacy of rapastinel (450 mg IV weekly or once every 2 weeks) versus placebo in the maintenance treatment of MDD as an adjunctive treatment to ongoing ADT, as measured by time to relapse during the DBTP

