## **6.0**

### **DEMOGRAPHICS AND OTHER BASELINE CHARACTERISTICS**

Demographic parameters (eg, age, race, ethnicity, sex, weight, height, body mass index) and other baseline characteristics will be summarized overall for the Open-label ITT Population and by treatment group for the Double-blind mITT Population.

Medical and surgical history, psychiatric history, previous treatment with psychotropic medication, and nondrug psychiatric treatment will be summarized overall for the Open-label Safety Population and by treatment group for the Double-blind Safety Population.

Prior medication is defined as any medication started before the date of the first dose of open-label IP. Concomitant medication during the OLTP is defined as any medication taken on or after the date of the first dose of open-label IP during the OLTP. Concomitant medication during the DBTP is defined as any medication taken on or after the date of the first dose of double-blind IP during the DBTP.

The use of prior and concomitant medications during the OLTP will be summarized by the number and percentage of patients receiving each medication within each therapeutic class for the Open-label Safety Population. Concomitant medications during the DBTP will be summarized by treatment group by the number and percentage of patients receiving each medication within each therapeutic class for the Double-blind Safety Population. Multiple medication use of the same therapeutic class by a patient will only be counted once. Concomitant medications started after the patient's last study visit during their last treatment period will not be summarized but will be included in the data listings.

Prior ADT treatment in the current episode, as recorded on the ATRQ collected in the lead-in studies, will be summarized by frequency counts and percentages for patients who took each ADT in adequate dose and duration, total number of ADT taken at adequate dose and duration (ie, 1, 2, 3 or more), and percentage of improvement reported (ie, < 25%, 25% to 49%, 50% to 75%, or >75%). For the OLTP, the summaries will be overall for the Open-label Safety Population. For the DBTP, the summaries will be by treatment group for the Double-blind Safety Population.

The *WHO Drug Dictionary Enhanced* will be used to classify prior and concomitant medications by therapeutic class and drug name.

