## **7.0 EXTENT OF EXPOSURE AND TREATMENT COMPLIANCE**

### **7.1 EXTENT OF EXPOSURE**

Exposure to open-label rapastinel for the Open-label Safety Population during the OLTP will be summarized for treatment duration, calculated as the number of days from the date of the first dose of open-label rapastinel taken to the date of the last dose taken during the OLTP, inclusive. Descriptive statistics will be presented.

Exposure to double-blind IP for the Double-blind Safety Population during the DBTP will be summarized for treatment duration, calculated as the number of days from the date of the first dose of double-blind IP taken to the date of the last dose taken during the DBTP, inclusive. Descriptive statistics will be presented by treatment group.

The number of IV doses of rapastinel administered to each patient during the OLTP will be summarized using descriptive statistics for the Open-label Safety Population.

Similarly, the number of IV doses administered to each patient during the DBTP will be summarized by treatment group, using descriptive statistics for the Double-Blind Safety Population.

The number and percentage of patients taking each qualifying ADT in the OLTP will be summarized for the Open-label ITT Population; the number and percentage of patients taking each qualifying ADT in the DBTP will be summarized by double-blind treatment group for the Double-Blind mITT Population. Mean daily dose and duration of previous treatment with each qualifying ADT will be summarized using descriptive statistics for the OLTP and by double-blind treatment group for the DBTP for the respective ITT or mITT populations.

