#### Missing month only

- If only the month is missing, the day will be treated as missing and both the month and the day will be replaced according to the above procedure.

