#### Missing day only

- If the month and year of the incomplete start date are the same as the month and year of the first dose of open-label IP, the day of the first dose of open-label IP will be assigned to the missing day.
- If either the year of the incomplete start date is before the year of the date of the first dose of open-label IP or if both years are the same, but the month of the incomplete start date is before the month of the date of the first dose of open-label IP, the last day of the month will be assigned to the missing day.
- If either the year of the incomplete start date is after the year of the date of the first dose of open-label IP or if both years are the same, but the month of the incomplete start date is after the month of the date of the first dose of open-label IP, the first day of the month will be assigned to the missing day.

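### The start-date rule for partly missing medication dates can set an already ongoing background antidepressant to begin on the first open-label dose, so previous ADT duration can only be understated

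*SAP*

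**What the plan says.** Section 15.8 fixes the scope: "For prior or concomitant medications, including background ADT, incomplete (ie, partially missing) start dates and/or stop dates will be imputed". The visible text has no separate rule for background ADT, so the branches of Section 15.8.1 apply to it:

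- Month and day missing, same year as the first open-label dose: "the month and day of the first dose of open-label IP will be assigned to the missing fields".
- Month and day missing, earlier year: "If the year of the incomplete start date is before the year of the first dose of open-label IP, 31 Dec will be assigned".
- Month only missing: "If only the month is missing, the day will be treated as missing and both the month and the day will be replaced", so it follows the two branches above.
- Day only missing, same month and year as the first open-label dose: "the day of the first dose of open-label IP will be assigned to the missing day".
- Day only missing, earlier month: the last day of the recorded month.

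The one override in Section 15.8.1 moves the start back to the stop date when the imputed start falls after it. A drug still being taken has no such stop date.

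Two planned outputs depend on the start date. Section 7.1 states: "Mean daily dose and duration of previous treatment with each qualifying ADT will be summarized using descriptive statistics", for the OLTP and by double-blind group. Section 6.0 states: "Prior medication is defined as any medication started before the date of the first dose of open-label IP".

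**The concern.** Section 2.0 limits all analyses to patients who completed a lead-in study, and Section 3.0 describes rapastinel as added to ADT that is ongoing. For a patient whose ADT was already running at open-label entry, a start date equal to the first open-label dose cannot be right.

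Placing an uncertain start at first dose has a purpose for adverse events (Section 15.7), where it errs towards counting the event as treatment-emergent. Section 15.8.1 uses the same wording for medications. For an ADT known to be ongoing, choosing the latest date protects nothing and pushes the error in one direction only.

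At stake is the description of background treatment: how long patients had been on their qualifying ADT, and whether that ADT appears in the prior-medication table.

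**Working it through.** The SAP gives no figure to reproduce, so the check applies the Section 15.8.1 rules to example dates. All dates below are assumptions. The count is also an assumption, because Section 7.1 gives no formula:

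previous duration = first open-label dose date − ADT start date

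A drug is prior under Section 6.0 only if its start is strictly before the first open-label dose.

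| What is missing | First open-label dose | True start | True days | Imputed start | Imputed days | Still prior? |
|---|---|---|---|---|---|---|
| Month and day, same year | 15 Jun 2017 | 10 Jan 2017 | 156 | 15 Jun 2017 | 0 | No |
| Month and day, same year | 15 Jun 2017 | 10 Apr 2017 | 66 | 15 Jun 2017 | 0 | No |
| Month and day, same year | 30 Nov 2017 | 10 Jan 2017 | 324 | 30 Nov 2017 | 0 | No |
| Day only, month of first dose | 15 Jun 2017 | 2 Jun 2017 | 13 | 15 Jun 2017 | 0 | No |
| Day only, earlier month | 15 Jun 2017 | 10 Jan 2017 | 156 | 31 Jan 2017 | 135 | Yes |
| Month and day, earlier year | 15 Jun 2017 | 1 Mar 2016 | 471 | 31 Dec 2016 | 166 | Yes |

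**Same-year branch.** The result is 0 for every true start in that year (1 day if both ends are counted). With a first dose on 1 Oct 2018 and only 2018 recorded, the imputed value is 0, while the true value can reach 273 days (1 Jan to 1 Oct).

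**Earlier-year branch.** With a first dose on 10 Jan 2018 and only 2017 recorded, the imputed value is 10 days (31 Dec 2017 to 10 Jan 2018). The recorded year alone allows 10 to 374 days (1 Jan 2017 to 10 Jan 2018 = 365 + 9).

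**Direction.** For a start before the first open-label dose, neither branch gives a date earlier than the true one. Imputed duration is therefore at most the true duration, and the errors cannot cancel across patients.

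**Effect of a midpoint.** With a first dose on 15 Jun 2017 (day 166 of the year) and only 2017 recorded, a start capped at the day before lies on days 1 to 165. The midpoint is day (1 + 165)/2 = 83, so duration is 166 − 83 = 83 days. The possible range is 1 to 165 days, so the error is at most 82 days in either direction. The current rule gives 0, with an error of up to 165 days, always downward.

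**The case against.** The strongest reply is that this is a common convention with little reach. An ongoing ADT still counts as concomitant in the OLTP under Section 6.0. Each qualifying ADT is tabulated separately under Section 7.1. ADT use in the current episode is reported from the ATRQ collected in the lead-in studies, and nothing visible sends those data through Section 15.8.1. The rule is the same for every arm and anchored before randomization. All of this stands and keeps the point small. It does not make the imputed date right for an ongoing ADT, nor the resulting duration usable.

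The reply also bars several stronger readings:

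- A reader might infer that every incomplete same-year date gives zero. It does not: a missing day in a known earlier month gives the last day of that month, an error of at most 30 days.
- A reader might take zero as established. Section 7.1 defines neither the formula nor the end date. If the double-blind summary counts to the first double-blind dose, the same-year branch would give roughly the open-label length, 8 to 16 weeks (56 to 112 days).
- A reader might infer that the open-label response is confounded. No visible model uses ADT duration, and Section 8.1 compares treatment groups by log-rank test and a Cox model with treatment group as the only explanatory variable. The table would misdescribe background treatment; no effect estimate would change.
- A reader might want a patient count. The SAP gives no share of incomplete ADT dates, and only the same-year or same-month subset reaches zero, so a number would be a guess.

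**Conclusion.** The point holds as a minor defect in a stated rule. For background ADT ongoing at open-label entry, Section 15.8.1 assigns the first open-label dose date when the month is missing in the same year, or the day is missing in the same month. That date conflicts with Sections 2.0 and 3.0 and drops the drug from the Section 6.0 definition of prior medication. With a missing month and an earlier year, the drug stays prior but the latest possible date is used. Both branches can only understate the previous ADT duration in Section 7.1.

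Per affected patient, the understatement in the examples runs from 13 to 324 days in the branches that give the first-dose date, and is 305 days (471 − 166) in the earlier-year example. Three assumptions carry this: duration is counted to the first open-label dose; the ADT predates that dose, which is inferred from its being ongoing in roll-over patients and is not stated as a start-date requirement; and the example dates are illustrative. How often it occurs is unknown. The primary and secondary analyses are unaffected.

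**What to change.** Add one sentence to Section 15.8.1: background ADT recorded as ongoing at open-label entry is exempt from the open-label anchor and from the 31 December rule. Its start is imputed within the recorded year or month, for example at the midpoint of the possible interval, and no later than the day before the first open-label dose.

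Use the day before the first lead-in IP dose as a tighter cap only where the partial date allows it and the ADT is known to predate the lead-in study. As a general cap it would fail: if the recorded year is the open-label year but lead-in dosing began the year before, no possible date remains. It would also assume an ADT requirement that the SAP does not state.

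The cost is that sentence and a small programming change. First open-label dose dates are already used in Section 15.8.1, and lead-in first-dose dates are already needed for the TEAE definition in Section 9.1. The midpoint is itself a convention: it removes the one-sided error but not the uncertainty for the individual patient.
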